#### **4.1.2 Exclusion Criteria**

Patients who meet any of the following criteria will be excluded from study entry:

- Known CD20-negative status at relapse or progression
- Prior allogeneic SCT
- Completion of autologous SCT within 100 days prior to Day 1 of Cycle 1
- Prior standard or investigational anti-cancer therapy as specified below:
  - Radioimmunoconjugate within 12 weeks prior to Day 1 of Cycle 1
  - Monoclonal antibody or antibody–drug conjugate within 4 weeks prior to Day 1 of Cycle 1

- Radiotherapy, chemotherapy, hormonal therapy, or targeted small-molecule therapy within 2 weeks prior to Day 1 of Cycle 1
- Clinically significant toxicity (other than alopecia) from prior therapy that has not resolved to Grade  $\leq 2$  (according to NCI CTCAE v4.0) prior to Day 1 of Cycle 1
- Grade 3b FL
- History of transformation of indolent disease to DLBCL (expansion-phase only)
  - History of transformation of indolent disease is allowed in the dose escalation phase.
- Central nervous system lymphoma or leptomeningeal infiltration
- Treatment with systemic corticosteroids  $> 20$  mg/day, prednisone or equivalent
  - Patients receiving corticosteroids  $\leq 20$  mg/day, prednisone or equivalent, for reasons other than lymphoma must be documented to be on a stable dose for at least 4 weeks prior to Day 1 of Cycle 1.
  - If corticosteroid treatment is urgently required for lymphoma symptom control prior to the start of study treatment, up to 100 mg/day of prednisone or equivalent may be given for a maximum of 5 days, but all tumor assessments must be completed prior to start of corticosteroid treatment.
- Clinical conditions requiring treatment with oral or parenteral anticoagulants or antiplatelet agents (e.g., chronic daily treatment with aspirin  $> 325$  mg/day, clopidogrel, warfarin, systemic low-molecular-weight heparin [LMWH]) unless treatment can be discontinued 7 days (or 5 half-lives) prior to initiation of study treatment (except used as flushes for indwelling catheters)
- Refusal of blood products and/or sensitivity to blood products
- History of severe allergic or anaphylactic reaction to humanized or murine monoclonal antibodies
- Known hypersensitivity or allergy to murine products or any component of the obinutuzumab, rituximab, idasanutlin, or venetoclax formulation
- Infection considered by the investigator to be clinically uncontrolled or poses an unacceptable risk to the patient upon the induction of neutropenia, that is, patients who are or should be on antimicrobial agents for the treatment of active infection such as the following:
  - Fungal infection with visceral involvement, other than mucosal candidiasis, with  $< 2$  weeks of appropriate systemic antifungal therapy
  - Bacterial infection with positive cultures within 7 days prior to initiation of study treatment
  - Patients who have received  $< 5$  days of appropriate therapeutic antibiotic therapy for an identified infection
  - Neutropenic fever considered infection related within 72 hours prior to initiation of study treatment

- History of symptomatic *C. difficile* infection that required treatment within 1 month prior to dosing
  - Upon clinical response to *C. difficile* treatment, the stool consistency and frequency must have returned to normal.

In all cases, the patient should be afebrile and hemodynamically stable for at least 72 hours at the time of study treatment initiation.

Caution should be exercised when considering the use of obinutuzumab or rituximab in patients with a history of recurring or chronic infections.

- Treatment with the following agents within 7 days prior to the first dose of venetoclax and idasanutlin:
  - Strong and moderate CYP3A inhibitors such as fluconazole, ketoconazole, and clarithromycin
  - Moderate CYP3A inducers such as bosentan
  - CYP2C8 substrates such as repaglinide
  - UGT1A3 inhibitor gemfibrozil
  - OATP1B1/3 substrates such as statin drugs
- Treatment with the following agents within 14 days prior to the first doses of venetoclax and idasanutlin
  - Strong CYP3A inducers such as rifampin (also a CYP2C8 inducer) and carbamazepine
- Chronic use of CYP2C8 or OATP1B1/3 substrates
- Consumption of grapefruit, grapefruit products, Seville oranges (including marmalade that contains Seville oranges), or star fruit within 3 days prior to the first dose of venetoclax
- Clinically significant history of liver disease, including viral or other hepatitis, current alcohol abuse, or cirrhosis (e.g., Child-Pugh class B and C)
- Current or history of HBV or HCV infection: positive for hepatitis B surface antigen (HBsAg), total hepatitis B core antibody (HBcAb), or hepatitis C virus (HCV) antibody at screening
  - Patients are eligible if both HBsAg and HBcAb are negative but tested positive for hepatitis B surface antibody (HBsAb) after vaccination.
- Known history of HIV-positive status
  - For patients with unknown HIV status, HIV testing must be performed at screening if not in contradiction with local regulations.
- History of PML
- Vaccination with a live virus vaccine within 28 days prior to Day 1 of Cycle 1

- History of other malignancy that could affect compliance with the protocol or interpretation of results, with the exception of the following:
  - Curatively treated carcinoma in situ of the cervix, good-prognosis ductal carcinoma in situ of the breast, basal- or squamous-cell skin cancer, Stage I melanoma, or low-grade, early-stage localized prostate cancer
  - Any previously treated malignancy that has been in remission without treatment for  $\geq 2$  years prior to enrollment
- Evidence of any significant, uncontrolled concomitant disease that could affect compliance with the protocol or interpretation of results, including significant cardiovascular disease (such as New York Heart Association Class III or IV cardiac disease, myocardial infarction within the previous 6 months, unstable arrhythmia, or unstable angina) or significant pulmonary disease (such as obstructive pulmonary disease or history of bronchospasm), or uncontrolled irritable bowel disease (i.e., Crohn disease, ulcerative colitis, diverticulosis-associated colitis, and Behçet disease)
- Nonmalignant medical illnesses that are uncontrolled or whose control may be jeopardized by study treatment, such as severe hereditary coagulation disorders or insulin-dependent diabetes mellitus that is not optimally controlled with medical management (e.g., presence of ketoacidosis)
- Major surgical procedure other than for diagnosis within 28 days prior to Day 1 of Cycle 1, or anticipation of a major surgical procedure during the study
- Inadequate hematologic function (unless due to underlying lymphoma), defined as follows:
  - Hemoglobin  $< 9$  g/dL
  - ANC  $< 1.5 \times 10^9$  cells/L
  - Platelet count  $< 75 \times 10^9$  cells/L
- Any of the following abnormal laboratory values (unless due to underlying lymphoma):
  - Calculated creatinine clearance  $< 50$  mL/min using the modified Cockcroft-Gault (see [Appendix 11](#))
  - Patients with clinically significant persistent electrolyte abnormalities, such as hypokalemia, hyperkalemia, hypocalcemia, hypercalcemia, hypomagnesemia, and hypermagnesemia of Grade  $> 1$  according to NCI CTCAE, v4.0
    - Treatment for correction of above electrolyte imbalances is permitted during screening to meet eligibility criteria.
  - AST or ALT  $> 2.5 \times$  ULN
  - Serum total bilirubin  $> 1.5 \times$  ULN (or  $> 3 \times$  ULN for patients with Gilbert syndrome)
  - INR or PT  $> 1.5 \times$  ULN in the absence of therapeutic anticoagulation
  - PTT or aPTT  $> 1.5 \times$  ULN in the absence of a lupus anticoagulant

- Pregnancy or lactation, or plans to become pregnant during the study  
Women of childbearing potential must have a negative serum pregnancy test result within 7 days prior to Day 1 of Cycle 1.
- Life expectancy <3 months
- Inability to comply with the study protocol, in the investigator's judgment

## **4.2 METHOD OF TREATMENT ASSIGNMENT**

This is a Phase Ib/II, open-label, multicenter, non-randomized study of obinutuzumab in combination with idasanutlin and venetoclax in patients with R/R FL and obinutuzumab or rituximab in combination with idasanutlin and venetoclax in patients with R/R DLBCL. Following determination of the MTDs with idasanutlin and venetoclax in combination with obinutuzumab, cohort(s) of patients with DLBCL will be opened to confirm the MTDs of idasanutlin and venetoclax in combination with rituximab. Following determination of the MTDs of idasanutlin and venetoclax in combination with obinutuzumab, cohort(s) of patients with FL will be opened to explore a different regimen (Regimen B, obinutuzumab alone at Cycle 1 and obinutuzumab in combination with idasanutlin and venetoclax at Cycles 2–6). During the dose-escalation phase, patients will be assigned to dosing groups through use of an interactive voice or Web-based response system (IxRS). During the expansion phase, all patients will be assigned to receive the RP2Ds with the selected regimen via IxRS. If eligible, patients will receive maintenance (FL patients) or consolidation (DLBCL patients) treatment (see Sections 3.1.2 and 3.1.3 for details).

Enrollment tracking will be performed through use of the IxRS. Prior to initiation of screening, study site personnel should confirm through the appropriate communication channel that the planned dose-escalation or expansion cohort is open for enrollment. After written informed consent has been obtained and preliminary eligibility has been established, the study site will submit documentation supporting eligibility to the Sponsor and obtain the Sponsor's approval to enroll the patient. Once the Sponsor reviews and approves a patient for enrollment, a patient number will be assigned and the patient will be enrolled via the IxRS. The Sponsor will communicate to the sites impending closure of screening for a particular disease cohort.

## **4.3 STUDY TREATMENT**

The investigational medicinal products (IMPs) for this study are obinutuzumab, rituximab, idasanutlin, and venetoclax and will be supplied by the Sponsor.

### **4.3.1 Formulation, Packaging, and Handling**

#### **4.3.1.1 Obinutuzumab**

Obinutuzumab will be provided as a single-dose, sterile liquid formulation in a 50-mL glass vial containing 1000 mg of obinutuzumab. For information on the formulation and handling of obinutuzumab, see the Obinutuzumab Investigator's Brochure and the pharmacy manual.

#### **4.3.1.2 Rituximab**

Rituximab will be supplied by the Sponsor as an IMP. Rituximab is packaged in 10-mL (100-mg) and 50-mL (500-mg) single-dose, pharmaceutical-grade glass vials at a concentration of 10 mg/mL of protein. The antibody is formulated for IV injection as a sterile product in a solution of sodium chloride (pH 6.5) containing polysorbate 80 and sodium citrate.

For information on the formulation and handling of rituximab, see the Rituximab IV Oncology Investigator's Brochure and the Rituximab Pharmacy Manual.

#### **4.3.1.3 Idasanutlin**

Idasanutlin will be supplied as film-coated tablets. Four different dose strengths of 50 mg (Ro 550-3781/F17), 200 mg (Ro 550-3781/F16), 300 mg (Ro 550-3781/F13), and 400 mg (Ro 550-3781/F14) were developed and optimized for use in clinical studies. For information on the formulation and handling of idasanutlin, see the Idasanutlin Investigator's Brochure.

#### **4.3.1.4 Venetoclax**

Venetoclax will be supplied as film-coated tablets. Two different strengths of 50 mg and 100 mg were developed and optimized for the use in clinical studies. For information on the formulation and handling of venetoclax, see the Venetoclax Investigator's Brochure.

### **4.3.2 Dosage, Administration, and Compliance**

The treatment regimens are summarized in [Table 1](#), [Table 2](#), [Table 5](#), and [Table 5](#) (see [Section 3.1](#)).

*Any dose modification should be noted on the Study Drug Administration electronic Case Report Form (eCRF). Cases of overdose, medication error, drug abuse, or drug misuse, along with any associated adverse events, should be reported as described in [Section 5.4.4](#).*

#### **4.3.2.1 Obinutuzumab**

[figure not shown]
Obinutuzumab will be administered by IV infusion at an absolute (flat) dose of 1000 mg on Days 1, 8, and 15 of the first cycle and on Day 1 of each subsequent cycle during induction treatment, and on Day 1 of every other month (i.e., every 2 months) during maintenance treatment (eligible patients with FL only) or during consolidation treatment (eligible patients with DLBCL only).

Obinutuzumab should be administered as an IV infusion through a dedicated line in an environment in which full resuscitation facilities are immediately available and under the close supervision of an experienced physician. Obinutuzumab infusions will be administered to patients according to the instructions outlined in [Figure 11](#) and [Figure 12](#). For patients with bulky lymphadenopathy, the infusion may be given extremely slowly over a longer period of time, or the dose may be split and given over more than 1 day.

No dose modification for obinutuzumab is allowed. Guidelines for treatment delays or discontinuation are provided in Section [5.1.8](#).

Premedication with a corticosteroid, antihistamine, and analgesic or antipyretic medication, as outlined in Section [4.3.2.5](#), is required to reduce the incidence and severity of IRRs. For anaphylaxis precautions, see [Appendix 10](#).

**Figure 11 Guidelines for Obinutuzumab Infusions: First Infusion**

[figure not shown]
IRR=infusion-related reaction.

a All patients should receive full premedication with an oral corticosteroid, antihistamine, and oral analgesic/anti-pyretic medication prior to the first obinutuzumab infusion. Refer to Section 4.3.2.5 for details.

b Supportive treatment should include acetaminophen/paracetamol and an antihistamine such as diphenhydramine, if not administered within the previous 4 hours. Intravenous saline may be indicated. For bronchospasm, urticaria, or dyspnea, patients may require antihistamines, oxygen, corticosteroids (e.g., 100 mg oral prednisone or equivalent), and/or bronchodilators. For anaphylaxis precautions, see Appendix 10.

**Figure 12 Guidelines for Obinutuzumab Infusions: Second and Subsequent Infusions**

IRR=infusion-related reaction.

a Patients should receive full premedication with an oral corticosteroid, antihistamine, and oral analgesic/antipyretic medication prior to the obinutuzumab infusion. Refer to Section 4.3.2.5 for details. In the case of a recurrent Grade 3 IRR, obinutuzumab may be discontinued at the discretion of the investigator, following an individual benefit–risk assessment.

b Patients who experience wheezing, urticaria, or other symptoms of anaphylaxis must receive full premedication prior to all subsequent doses.

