#### **4.3.2.5 Premedication**

Patients must receive premedication as outlined in [Table 7](#).

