**Table 7 Premedication (cont.)**

Timepoint	Patients Requiring Premedication	Premedication	Administration
Cycle 1, Days 8 and 15 (for patients receiving obinutuzumab); Cycles 2 and beyond, Day 1	Patients with no IRR during the previous infusion	
 
Oral analgesic/anti-pyretic medication c
 
	Administer ≥ 30 minutes prior to obinutuzumab or rituximab infusion. For patients receiving rituximab who do not experience any IRR with their previous infusion, premedication may be omitted at the investigator's discretion.
	
 
Patients with Grade 1 or 2 IRR during the previous infusion
 
	
 
Antihistamine drug b
 
Oral analgesic/anti-pyretic c
 
	Administer ≥ 30 minutes prior to obinutuzumab or rituximab infusion.
	
 
Patients with Grade 3 IRR, wheezing, urticaria, or other symptoms of anaphylaxis during the previous infusion
 
	
 
Oral corticosteroid a
 
	Administer ≥ 1 hour prior to obinutuzumab or rituximab infusion.
	
 
Patients with bulky disease
 
	
 
Antihistamine drug b
 
Oral analgesic/anti-pyretic medication c
 
	Administer ≥ 30 minutes prior to obinutuzumab or rituximab infusion.
	Patients at high risk of TLS (see Section 5.1.7.2)	
 
Consider hospitalization if patient is still considered at high risk of TLS (see Section 5.1.7.2), refer to premedication as defined for Cycle 1.
 
	Refer to Section 5.1.7.2.
Cycles 1 to 6	All patients receiving idasanutlin	
 
Second-generation anti-emetic treatments, such as palonosetron, ondansetron, or granisetron
 
	Administer per individual drug prescribing information.
Cycles 1 to 6	All patients	
 
No premedication for diarrhea
 
	Not applicable
	Patients with previous episode of Grade ≥ 3	
 
Loperamide 4 mg orally
 
	Loading dose 30 minutes before first administration of study drug.

---

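### After anaphylaxis-type symptoms, Figure 12 footnote b keeps full obinutuzumab premedication for every later dose, but Table 7 steps it down after one infusion without an IRR (patients without bulky disease)

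*Protocol*

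**What the plan says.** The protocol gives obinutuzumab premedication rules in two places, and both bind.

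- **Figures 11 and 12.** Section 4.3.2.1 directs that obinutuzumab infusions follow these figures. Figure 12, for the second and later infusions, carries footnote b: "Patients who experience wheezing, urticaria, or other symptoms of anaphylaxis must receive full premedication prior to all subsequent doses". Figure 11 footnote a shows what full premedication is: "All patients should receive full premedication with an oral corticosteroid, antihistamine, and oral analgesic/anti-pyretic medication prior to the first obinutuzumab infusion".
- **Table 7.** Section 4.3.2.5 says: "Patients must receive premedication as outlined in" Table 7. Section 4.3.2.1 also sends the reader there: "Premedication with a corticosteroid, antihistamine, and analgesic or antipyretic medication, as outlined in Section" 4.3.2.5. So does footnote a of each figure. Footnote b contains no pointer.

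After the first dose, the Table 7 block is headed "Cycle 1, Days 8 and 15 (for patients receiving obinutuzumab); Cycles 2 and beyond, Day 1". Its reaction-based rows are:

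- "Patients with no IRR during the previous infusion": oral analgesic/antipyretic only.
- "Patients with Grade 1 or 2 IRR during the previous infusion": antihistamine and oral analgesic/antipyretic.
- "Patients with Grade 3 IRR, wheezing, urticaria, or other symptoms of anaphylaxis during the previous infusion": oral corticosteroid, with the antihistamine and analgesic/antipyretic printed on the adjoining bulky-disease line.

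Bulky disease is listed without reference to the previous infusion. No row or footnote of Table 7 carries an earlier anaphylaxis-type reaction beyond the next infusion.

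**The concern.** Footnote b has a lasting memory: once the symptoms have occurred, every later dose is covered. Table 7 looks back one infusion only. After a single uneventful infusion the two give different answers for the same patient, and the protocol states no order of precedence.

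Table 7 is where a site is sent to look up premedication. A site that reads it as complete will drop the corticosteroid and antihistamine. A patient who has already shown symptoms of anaphylaxis could then receive further 1000 mg infusions with an analgesic/antipyretic alone, although the protocol's own stricter rule requires all three drugs. What is at stake is the safety of individual patients on obinutuzumab: the follicular lymphoma (FL) cohorts, and the patients with diffuse large B-cell lymphoma (DLBCL) in the Regimen A escalation cohorts.

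**Working it through.** The plan states no figure to reproduce. The check follows one patient through both rules and counts the infusions at which they part.

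**Inputs**

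- Obinutuzumab infusions in induction (Section 4.3.2.1): Days 1, 8 and 15 of Cycle 1, then Day 1 of Cycles 2 to 6. That is 3 + 5 = 8.
- Footnote b: full premedication at every infusion after the symptoms.
- Table 7: corticosteroid only if the symptoms occurred at the infusion just before.
- Assumed patient: no bulky disease, symptoms at infusion k, no IRR at any later infusion.

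**Worked case, k = 2 (symptoms on Cycle 1 Day 8)**

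1. Before infusion 3 (Cycle 1 Day 15), the symptoms were at the previous infusion. Both rules call for the corticosteroid.
2. Infusion 3 passes without an IRR.
3. Before infusion 4 (Cycle 2 Day 1), footnote b still requires all three drugs. Table 7 now places the patient in its no-IRR row, which lists one.
4. The same difference recurs at infusions 5 to 8.

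**Count**

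Remaining infusions = 8 − k. Footnote b covers 8 − k of them and Table 7 covers 1, so they differ at (8 − k) − 1 = 7 − k.

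| Symptoms at infusion | Remaining | Footnote b | Table 7 | Differ |
|---|---|---|---|---|
| 2 | 6 | 6 | 1 | 5 |
| 3 | 5 | 5 | 1 | 4 |
| 1 (only if footnote b reaches back to it) | 7 | 7 | 1 | 6 |

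If a later infusion produces a Grade 1 or 2 IRR without these symptoms, Table 7 gives the antihistamine and analgesic/antipyretic at the next one, so only the corticosteroid is missing there.

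**What the count depends on**

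- The Figure 12 chart is not shown. Its title covers second and later infusions, so the infusion 1 line is conditional.
- The third Table 7 row is broken in the available text, and reading it as one three-drug tier is an inference. The corticosteroid count of 1 does not need that inference, because the corticosteroid is printed beside the previous-infusion trigger.
- Infusions after induction are not in the table. FL maintenance is every 2 months for 24 months, so up to about 24 / 2 = 12 more infusions fall under footnote b.

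**The case against.** The best answer is that the protocol already contains the safeguard. Section 4.3.2.1 makes Figure 12 an operative instruction for every later infusion, so a site using Table 7 alone is not following the protocol. Table 7 is shared by both antibodies and could be a general scheme to which drug-specific rules add. Table 6 is likewise stricter than Table 7 for rituximab, calling for full premedication after any reaction at the prior infusion. Since giving all three drugs meets both rules, this could be called a missing cross-reference.

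Part of this stands. A reader might infer that the two rules cannot both be obeyed, or that the protocol leaves these patients without any full-premedication rule. Neither is so. But the general-scheme reading is only an inference: the Table 7 block names obinutuzumab, its rows carry no exception, and nothing ranks one source above the other. Table 6 also limits rituximab's full premedication to the period until no further IRR occurs, which suggests that the longer duration for obinutuzumab was intended.

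The objection on reach stands in full. The conflict needs obinutuzumab, no bulky disease, symptoms that do not end treatment, and a later infusion with no IRR or a milder one. Section 5.1.1.1 says IRRs occur mainly at the first infusion, the case in which footnote b's coverage cannot be confirmed. Section 4.1.2 excludes patients with a history of severe allergic reaction to humanized or murine antibodies, and infusions require resuscitation facilities and experienced supervision.

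**Conclusion.** The inconsistency is in the current text and is worth correcting, as a minor matter. For an obinutuzumab patient without bulky disease, with symptoms at infusion 2 and no later IRR, footnote b requires full premedication at 6 of 6 remaining induction infusions and Table 7 at 1 of 6. These are counts within a constructed patient. The documents give no share of patients with such symptoms, so no patient number follows.

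Three wider readings are not supported:

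- A reader might infer that patients with diagnosed anaphylaxis are under-treated. Section 4.6.2 and Table 18 stop study treatment for anaphylaxis and Grade 4 IRR, so they are outside this point.
- A reader might extend it to rituximab. Footnote b belongs to the obinutuzumab figure, and Table 6 expressly allows step-down.
- A reader might expect an effect on dose-limiting toxicity or complete response. Nothing in the documents supports one.

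The conclusion rests on footnote b as written and on the previous-infusion wording of Table 7. It does not depend on the missing chart or on how the broken row is rejoined, except for the conditional infusion 1 case.

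**What to change.** Leave the Table 7 rows as they are and attach one footnote to the three reaction-based rows (no IRR; Grade 1 or 2 IRR; Grade 3 IRR or anaphylaxis-type symptoms). It should say that, once a patient on obinutuzumab has had wheezing, urticaria or another symptom of anaphylaxis, full premedication (oral corticosteroid, antihistamine and oral analgesic/antipyretic) is mandatory before each later obinutuzumab dose, whatever happened at the previous infusion, and refer to Figure 12 footnote b. A footnote is safer than rewording the rows, because it leaves the Grade 3 IRR, bulky-disease and rituximab instructions untouched. Figure 12, Section 4.6.2 and Table 18 need no change.

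The cost is one footnote, plus extra corticosteroid and antihistamine doses at sites that would otherwise have followed Table 7. Per affected patient that is up to 5 in induction (6 if the symptoms came at infusion 1) and, in FL, up to about 12 more over 24 months of maintenance. Repeated steroid exposure is therefore not trivial for such a patient, but footnote b already requires all of it. No new visits, procedures or patients are needed.
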